## **Overall Study Objectives**

We will conduct a pilot randomized controlled trial with an embedded qualitative component with the following objectives:

- To evaluate the feasibility, safety, and preliminary effectiveness of an interdisciplinary synchronous telerehabilitation program consisting of video-based individualized physiotherapy (PT), occupational therapy (OT), and/or speech language pathology (SLP) sessions, compared with current standard-of-care, on physical function, cognitive function, confidence to self-manage care, and quality of life for participants who are concurrently undergoing radiation therapy for glioma,
- To evaluate the feasibility of administering outcome measures of quality of life, recovery of impairment, fatigue and survival for a future definitive study
- 3. To understand the experiences of participants with telerehabilitation including the perceived impact on quality of life, as well as barriers and facilitators to participation

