## **Explanatory Variables to Characterize the Population:**

Demographic and medical variables to characterize the participant population will be collected at baseline and will include age, sex/gender, place of residence, education, postal code, occupation, race and ethnicity, presence of caregiver at residence, duration of radiation therapy, and medical comorbidities and medications. To reduce the time demands placed on participants, a research assistant will collect the variables whenever possible from chart review, and ask participants to provide information on the variables not available from chart review.

Table 1. Measurement Tools and Testing Schedule

Base-	4W	W8	12W	26W
line	`	(100	(100	(160
(100	min)	min)	min)	min)
min)				

Participant Demographic and Medical Information Form	Х				
Participant Personal Information Form	Х				
General Outcomes					
Feasibility and Safety Outcomes		Х	Х	Х	Х
Survival and Progression-Free Survival		Х	Х	Х	Х
EuroQol-5 Dimension 5 Level (EQ-5D-5L)	Х	Х	Χ	Х	Х
Fatigue Severity Scale	Х	Х	Χ	Х	Х
Physical outcomes measures					
Berg Balance Scale	Χ	Х	Χ	Х	X
Timed Up and Go Test	Χ	X	Χ	X	X
3m Walk Test	Х	X	Χ	X	X
The Arm Capacity and Movement Test (ArmCAM)	Х	Х	Χ	Х	Х
Cognitive tests					
Brief Test of Adult Cognition by Telephone (BTACT)	Х	Х	Χ	Х	Х
Brief Visuospatial Memory Test – Revised (BVMT)	Х	Х	Х	Х	Х
Sustained Attention to Response Task (SART)	Х	Х	Х	Х	Х
Wechsler Test of Adult Reading (WTAR)	Х	Х	Χ	Х	Х
Qualitative component					
Semi-structured Interview (telerehab group only)					Х

The majority of our outcome measures are self-report measures, which participants can either complete themselves and/or with assistance from a helper or research study staff based on participants' preferences. The outcome measures can be administered via a REDCap survey link sent to participants to enter their answers directly into REDCap or with assistance from a helper if they need it or via an online videoconference or telephone call between participants and study staff for direct entry of participants' answers into REDCap by research study staff (whichever method participants prefer).

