## Secondary Outcomes

Secondary outcomes (e.g. balance, mobility, quality of life, mood, etc.) are continuous in nature and will be analyzed using linear regression, adjusted for baseline. Time to all-cause mortality, time to disease specific mortality, and time to disease progression will be analyzed using Kaplan Meier estimators and logrank tests.

Disease and demographic factors that may influence protocol attrition and adherence will be analyzed using a generalized linear mixed effects model with an assumed unstructured covariance matrix structure and robust sandwich estimation.

To assess the safety of the protocol, the number, type, and severity of SA events will be reported as a cumulative incidence and compared between treatment arms using a Poisson regression.

Since these analyses are hypothesis generating, complete-case analyses will be used, p-values will not be listed and 95% confidence intervals of estimates and change scores will be used instead so the study results can be interpreted in context. The standard deviation of changes in secondary outcome measures will be used for sample size calculations for future full-scale studies.

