## Missing Data

Missing data for secondary measures will be assessed for quantity and nature of missingness. As secondary analyses are hypothesis generating, whole case analysis will be used even if >5% are missing data. Although the baseline values are also required for the secondary outcome analysis, we anticipate missingness

will be extremely infrequent as REDCap will be used for data collection and missing completely at random (MCAR) so that no bias will be incurred by dropping those cases from the analysis. Participants that drop out prior to completion of protocol will be right censored for survival analyses.

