### **Definition of a Serious Adverse Event**

A SAE is defined as an AE that results in any of the following outcomes:

- Death
- Life-threatening situation (participant was in immediate risk of death at the time of the event. However, an event that might have hypothetically caused death if it was of greater severity is not included.)
- New in-patient hospitalization or prolongation of existing hospitalization
- Persistent or significant disability or incapacity
- Important medical events not resulting in death, be life-threatening, or requiring hospitalization but may jeopardize the participant and may require medical or surgical intervention to prevent one of the above outcomes (based upon appropriate medical judgment)

Handling of Serious Adverse Events Principal investigators will be responsible for initiating appropriate medical care of participants during the study, in connection with trial procedures and assessments, and for monitoring the safety of participants.

All SAEs will be assessed during the course of the trial. At the beginning of every assessment session participants will be asked if they have experienced any AEs. Therapists routinely ask patients about adverse events that occur as the result of therapy, and they will be asked to relay this information to the Principal Investigators. In case an SAE is reported, the delegated study clinician who examines and evaluates the participant will determine the event's causality to the trial's procedures, based on temporal relationship and his/h r clinical judgment. It is the responsibility of the Principal Investigators to ensure all SAEs are assessed to determine causality, that is, to determine the likelihood that the SAE was caused by a study intervention.

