## **Documenting Serious Adverse Events**

Pre-existing conditions will be recorded at the baseline visit following participant enrolment (including start date of the condition, frequency, and severity). After the participant signs the informed consent form any worsening of these conditions will be documented.

SAEs experienced by the participant between the signing of the Informed Consent and completion of the final follow-up appointment (the 26-week visit) will be recorded in the electronic case report form (eCRF).

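### Progression-free survival is scheduled but never analysed: the analysis section substitutes time to progression and adds disease-specific mortality, for which no attribution of death is described

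*Protocol*

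**What the plan says.** The protocol describes its time-to-event outcomes in four places.

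- **Overall Study Objectives.** The second objective is "To evaluate the feasibility of administering outcome measures of quality of life, recovery of impairment, fatigue and survival for a future definitive study". Survival is named. Progression and disease-specific death are not.
- **Table 1, Measurement Tools and Testing Schedule.** One row, "Survival and Progression-Free Survival", is marked for weeks 4, 8, 12 and 26.
- **Statistical Analysis Plan, Secondary Outcomes.** "Time to all-cause mortality, time to disease specific mortality, and time to disease progression will be analyzed using Kaplan Meier estimators" and logrank tests.
- **Missing Data.** "Participants that drop out prior to completion of protocol will be right censored for survival analyses". This is the only censoring rule, and it does not say how a death is handled when the endpoint is progression or death from glioma.

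Death counts as a serious adverse event (SAE), and SAEs are entered in the eCRF from consent to the 26-week visit. The causality assessment of an SAE is defined as "to determine the likelihood that the SAE was caused by a study intervention", and the grades that follow are worded in terms of trial procedures.

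**The concern.** The schedule and the analysis should describe the same endpoints, and here they agree on only one. PFS is to be collected but has no analysis. Time to progression takes its place, and disease-specific mortality is analysed without appearing in the schedule or the objectives.

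The difference is more than a label. In PFS, a participant who dies without progression has had the event. In time to progression, that participant has not, and a standard Kaplan-Meier analysis censors at the date of death. Censoring assumes that those who died had the same later risk of progression as those who stayed under observation. In glioma of any grade, where death and progression share a cause, that assumption is hard to defend.

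Disease-specific mortality also requires each death to be attributed to glioma or to something else. If that is not arranged before enrolment, it may have to be reconstructed afterwards. Since the pilot is meant to show whether outcome measures, survival among them, can be administered in a definitive trial, the endpoint collected and the endpoint reported should be the same.

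**Working it through.** **Related figure in the plan.** The protocol states no event count, hazard ratio or event rate for any time-to-event endpoint. The only related figure is the sample size of 54, based on a third (33%) of 163 patients per year: 0.33 × 163 = 53.8, or 163 / 3 = 54.3. It reproduces.

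**The endpoints side by side.**

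| Endpoint | In Table 1 | In the analysis section |
|---|---|---|
| Death from any cause | Yes (survival) | Yes |
| Progression-free survival | Yes | No |
| Time to progression | No | Yes |
| Disease-specific mortality | No | Yes |

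**Source for cause of death.** The visit lists, Table 1, the chart variables and the SAE sections describe no attribution of death to glioma. The SAE grades mention concomitant disease and other etiology, but only as alternatives to trial procedures. They do not separate glioma deaths from other deaths. The fields of the eCRF and of the Medical Information Update Form are not shown.

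**Size of the difference between the endpoints.** The rates here are assumptions. Let *p* be the proportion who progress by week 26 and *d* the proportion who die without progression, with constant competing hazards over 26 weeks.

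- PFS event proportion = *p* + *d*.
- Total cumulative hazard = −ln(1 − *p* − *d*), of which the progression share is *p* / (*p* + *d*).
- Kaplan-Meier progression estimate with deaths censored = 1 − (1 − *p* − *d*)^(*p*/(*p*+*d*)).

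Example: with *p* = 0.30 and *d* = 0.15, −ln(0.55) = 0.598. The progression share is 0.598 × 0.30/0.45 = 0.399, and 1 − exp(−0.399) = 0.329, against a true cumulative incidence of 0.30.

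For *p* = 30% and 54 participants:

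| Death without progression | Progression events | PFS events | PFS event proportion | Kaplan-Meier progression |
|---|---|---|---|---|
| 2% | 16.2 | 17.3 | 32% | 30.3% |
| 5% | 16.2 | 18.9 | 35% | 30.9% |
| 10% | 16.2 | 21.6 | 40% | 31.8% |
| 15% | 16.2 | 24.3 | 45% | 32.9% |

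With *p* from 15% to 45% and *d* from 2% to 15%, PFS gains 54 × 0.02 = 1.1 to 54 × 0.15 = 8.1 events over time to progression. The Kaplan-Meier estimate exceeds the cumulative incidence by 0.2 points (15.2% against 15%) to 4.7 points (49.7% against 45%).

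**The case against.** The best case for leaving the text alone is that little depends on it. This is a 54-person pilot whose primary outcome is completion at week 8. Survival endpoints are not in the protocol's list of secondary outcomes. The analyses are called hypothesis generating, with no p-values to be listed. Rules for competing deaths and attribution are often left to a separate statistical analysis plan, which is not at hand. Censoring at death is also inferred from the named method, since the protocol does not state it. All of this limits the weight of the point. It does not remove the disagreement between Table 1 and the analysis section, which is in the text itself, and a later plan cannot ensure that cause of death was recorded as deaths occurred.

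A reader might infer more than the documents support:

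- **That none of the endpoints match, or that deaths are dropped.** All-cause mortality matches the survival item, and every observed death is an event in that analysis.
- **That progression will look rarer.** Time to progression has fewer events than PFS, but that compares two endpoints. Against its own cumulative incidence, progression is overstated when deaths are censored.
- **That both analysed endpoints need a cause of death, or that disease-specific mortality cannot be derived.** Only disease-specific mortality needs a cause. Deaths reach the eCRF as SAEs, and the form fields are not shown, so the most that can be said is that no attribution is described.
- **That events will be dated up to 14 weeks late** (26 − 12 = 14). This would follow only if events were dated to the visit, which the protocol does not say. Table 1 shows when status is collected and says nothing about which date is assigned.

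**Conclusion.** The point stands in a limited form. PFS is scheduled and has no planned analysis. The endpoint analysed in its place does not count death without progression as an event. Disease-specific mortality is analysed without any described attribution of death to glioma. These are comparisons of the protocol with itself and need no outside figure.

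The size does rest on assumptions: the two ranges of event rates, constant hazards, and censoring of deaths as Kaplan-Meier is ordinarily used. On that footing the choice of endpoint moves about 1 to 8 events among 54 participants, and the Kaplan-Meier overstatement is at most about 5 percentage points. The reported result would change, but no decision rule in the protocol depends on it. The correction is still worth making, because it is cheap and any capture of cause of death has to be settled before enrolment.

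**What to change.** In Statistical Analysis Plan, Secondary Outcomes, replace time to disease progression with progression-free survival, defined as progression or death from any cause, whichever comes first. This matches Table 1. Keep time to death from any cause as it is.

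For disease-specific mortality, choose one of two courses. Either delete it, or record the cause of each death prospectively, add the item to the schedule, and report the cumulative incidence of death from glioma with other deaths treated as competing events.

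The cost is one sentence in the analysis section and, if disease-specific mortality is kept, one form item and its attribution. No visits are added. The chart review now in the protocol covers baseline variables only, so if cause of death is to come from charts, that use has to be stated.

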## **Secondary Outcomes**

- Recruitment Screening and recruitment efficiency, number of participants recruited, percentage of patients approached who consent to the trial
- 2. **Adherence to interventions** Percentage of rehab sessions attended, participant characteristics associated with adherence, percentage of participants who used BrainHQ/exercise programs and how much
- 3. **Retention** Follow-up rates, time needed for data collection
- 4. **Participant Experience** We will conduct semi-structured qualitative interviews with participants to better understand their telerehab experiences, the perceived impact of the intervention on quality of life, and barriers/facilitators for their participation in the intervention.

**Safety** - percentage of patients who experience adverse events, percentage of rehab sessions in which adverse events occurs, and adverse event type, severity and relatedness across both intervention groups.

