#### Risks related to telerehab:

Risk of falls, injury and cardiac events such as dysrhythmia, exertional angina, and muscular/joint strains. Telerehab groups will be supervised and emergency contact information will be provided by participants. Participants will obtain physician clearance for exercise and will have a caregiver present during telerehab sessions. All telerehab sessions provided as part of this study will be provided by specialized physiotherapists, occupational therapists and speech language pathologists with training in neuro-rehabilitation working in the Brain Rehab program, and they will be adhering to all Brain Rehab Program policies and procedures on safety during telerehab.

Principal Investigators will review and classify all adverse events as to severity, whether it was expected or not, and whether it was related to the intervention. Recruitment rate, dropouts at all stages, and reasons for non-completion will also be tracked.

Adverse events related to the telerehabilitation assignment or to other causes will be adjudicated by the PIs.

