## **Determining causality of Serious Adverse Events**

Degree of certainty about causality will be graded as follows:

- **Definitely Related:** Clear evidence to suggest a causal relationship and other possible contributing factors can be ruled out.
- **Probably Related:** Evidence to suggest a causal relationship and the influence of other factors is unlikely.
- Possibly Related: Some evidence to suggest a causal relationship but the influence of other factors may have contributed to the event.
- **Unlikely:** The temporal relationship to the trial procedures makes a causal relationship improbable and/or the SAE is more likely due to other factors such as concomitant medication(s) or concomitant disease(s).

• **Not related:** The SAE is completely independent of trial procedures, and/or evidence exists that the event is definitely related to another etiology.

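### Safety is defined on all adverse events with relatedness, but the only planned between-arm comparison covers 'SA events' and leaves relatedness out

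*Protocol*

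**What the plan says.** Safety is part of the first aim under Overall Study Objectives. The safety item under Outcome Measurements, Secondary Outcomes, is the "percentage of patients who experience adverse events, percentage of rehab sessions in which adverse events occurs, and adverse event type, severity and relatedness", for both groups. It is not limited to serious events.

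Under Statistical Analysis Plan, Secondary Outcomes, the safety analysis is that "the number, type, and severity of SA events will be reported as a cumulative incidence and compared between treatment arms", using Poisson regression. The abbreviation SA is not explained; elsewhere the protocol writes AE or SAE.

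On recording, Documenting Serious Adverse Events sends to the eCRF the "SAEs experienced by the participant between the signing of the Informed Consent and completion of the final follow-up appointment" at week 26. For the same window, Reporting Serious Adverse Events has AEs reported to the principal investigator. On causality, the principal investigators must "ensure all SAEs are assessed to determine causality", and the lowest grade of the five-level scale reads "The SAE is completely independent of trial procedures".

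The section on telerehabilitation risks lists "Risk of falls, injury and cardiac events such as dysrhythmia, exertional angina, and muscular/joint strains". It also has the principal investigators classify every AE by severity, expectedness and relatedness.

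**The concern.** The outcome and its analysis cover different sets of events. If SA means serious adverse, the stated comparison excludes any fall or strain that does not lead to death, a threat to life, admission, lasting disability or an important medical event. Many of the harms that the protocol foresees from exercise therapy would fall outside those criteria. In people receiving radiation for glioma, it is reasonable to expect the tumour and its treatment to account for many SAEs. An SAE comparison that does not separate related from unrelated events is therefore a blunt measure of what the therapy does.

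This bears on the purpose of the trial. The Rationale cites poorer outcomes with very early rehabilitation after stroke as a reason to study timing, and the pilot is meant to inform a larger study. Usual care includes exercise instructions, so falls and strains can occur in both arms and a comparison has meaning.

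**Working it through.** The protocol states no figure to reproduce here: it gives no AE or SAE rate and no precision target for safety. The check is a cross-reading, followed by two pieces of context arithmetic.

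**1. The sections side by side**

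| Step | All AEs | SAEs |
|---|---|---|
| Outcome definition (Outcome Measurements, Secondary Outcomes) | Yes: "adverse event type, severity and relatedness across both intervention groups", plus patient and session percentages | Included within AEs |
| Asked about (Definition of a Serious Adverse Event; 8-, 12- and 26-Week Evaluation) | Yes, at every assessment; therapists also relay events | Yes |
| Classified for relatedness (Risks related to telerehab) | Yes, by the principal investigators, no scale named | Yes, with a five-level scale in a separate section |
| eCRF entry | Pertinent information, in Following up on Adverse Events; no window | Explicit rule, consent to week 26 |
| Descriptive summary (Trial Safety, Fidelity and Implementability Analyses) | Number and type | Included within AEs |
| Comparison between arms (Statistical Analysis Plan) | None stated | Number, type and severity; no relatedness |

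**2. One event traced through the text**

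Take a joint strain that needs no admission. The participant is asked about AEs at the next assessment, the event is reported to and classified by the principal investigators, pertinent details go to the eCRF, and it appears in a count by type. It is not an SA event as most naturally read, so it enters no arm comparison. It is outside the windowed eCRF rule and the wording of the graded scale. No sentence says that the record shows whether it happened during a study session.

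**3. How much an SAE comparison could say**

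The event rates are assumed. The sample is 27 per arm (Sample Size). With E = 27 × rate events in each arm and an observed rate ratio of 1, the approximate 95% interval is exp(±1.96 × √(2/E)).

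| Assumed events per participant | E per arm | √(2/E) | 95% interval |
|---|---|---|---|
| 0.1 (SAE) | 2.7 | 0.861 | 0.19–5.40 |
| 0.2 (SAE) | 5.4 | 0.609 | 0.30–3.30 |
| 0.3 (SAE) | 8.1 | 0.497 | 0.38–2.65 |
| 0.5 (all AE) | 13.5 | 0.385 | 0.47–2.13 |
| 1.0 (all AE) | 27 | 0.272 | 0.59–1.70 |
| 2.0 (all AE) | 54 | 0.192 | 0.69–1.46 |

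This takes equal follow-up and no overdispersion. Repeated events in the same person would widen every row, and the approximation is rough at the smallest counts.

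**4. The session-level measure**

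Twice-weekly sessions for 8 weeks give 2 × 8 = 16 per discipline. With one to three disciplines, that is 16 to 48 per participant, or 27 × 16 = 432 to 27 × 48 = 1,296 scheduled sessions in the telerehabilitation arm. Usual care has no study sessions. This measure can be described but not compared between arms.

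**The case against.** The best reply is that non-serious events are well covered. They are asked about at every assessment, noted at weeks 8, 12 and 26, relayed by therapists, reported to the principal investigators, classified for relatedness and counted by type. A section headed for SAEs naturally speaks of SAEs and does not exclude other events, and the follow-up section sends AE information to the eCRF. Form fields and tabulations usually belong in the case report form or a separate analysis plan, which is not at hand. Finally, therapists ask about events only where study therapy is given, so an all-AE comparison risks unequal detection. SAEs are less exposed to that, and confining the formal comparison to them is defensible in a pilot of 54 that reports no p-values.

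Much of this stands, and it rules out three stronger readings:

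- A reader might infer that only serious events are graded for causality. The telerehabilitation risk section contradicts this; only the five-level scale and the duty stated beside it are worded for SAEs.
- A reader might infer that only serious events reach the eCRF, or that the session percentage cannot be produced. No sentence says so. AE entry and session linkage are left unassured, not excluded.
- A reader might infer that the harms of exercise therapy are missed. They are collected and summarised.

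What the reply does not remove is the mismatch itself. The protocol states a between-arm safety analysis, and that analysis does not match the outcome it defines. This is not detail left to another document. The detection argument is sound, but the protocol does not make it, and it is better met by the choice of data source than by dropping non-serious events from the comparison.

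**Conclusion.** The point holds as an inconsistency that should be corrected. The safety outcome covers all AEs with relatedness in both arms; the only stated comparison covers SA events without relatedness. Followed as written, AEs are collected and counted by type, but non-serious falls and strains get no planned arm comparison and no assured, uniformly graded record.

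The conclusion about the comparison rests on reading SA as serious adverse. If the term was meant to cover all AEs, that gap closes, but the omission of relatedness and the uneven recording rules remain. The size can only be illustrated. At the assumed SAE rates, the interval around a ratio of 1 runs from a roughly fivefold to a two-and-a-half-fold difference in either direction. Adding non-serious events narrows it but leaves it wide. Safety is a stated objective but not the primary outcome, and nothing here affects the feasibility result.

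**What to change.** - **Statistical Analysis Plan, Secondary Outcomes.** Define SA events. Report and compare both all AEs and SAEs by arm: participants with at least one event, and event rates, each with a 95% confidence interval. Show related events separately.
- **Documenting Serious Adverse Events.** State that all AEs from consent to week 26 are entered in the eCRF with severity, seriousness, relatedness and whether they occurred in a study session.
- **Determining causality of Serious Adverse Events.** Apply the existing five-level scale to all AEs, so that the classification already required of the principal investigators is uniform.
- **Session measure.** Report the percentage of sessions with an AE descriptively, for the telerehabilitation arm only.
- **Source of events.** Base the arm comparison on the assessment-visit questioning common to both arms, and show therapist-relayed events separately, because that route exists only in the active arm.

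The cost is wording changes in these sections, AE fields in the eCRF and some extra data entry. The questioning and classification are already planned. Even with these changes, 27 per arm will give wide intervals, and the report should say so.

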#### Randomization

Participants will be stratified for glioma grade (grade <3, grade=4) and then randomly assigned to the 2 intervention groups using a 1:1 allocation ratio block design. The schedule will be randomly generated using the PLAN procedure (SAS 9.4, SAS Institute, USA).

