## **Study Sample Size and Statistical Analysis Sample Size**

A sample of 54 participants, 27 per arm, is planned for this study based upon an expected recruitment rate of a third (33%) of glioma patients seen in recruiting clinics (163 patient per annum). Feasibility trials are recommended to recruit between 20 to 50 participants per arm to adequately investigate if a protocol is feasible or not and a minimum of 22 participants per arm is required for precision

of the variance estimation. Loss to follow-up (LOF) will be analyzed as the primary outcome and the sample size will not be adjusted for LOF.

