## **Documenting participant withdrawal**

In all circumstances, reasons for withdrawal will be collected and all participants will be followed through to the trial's conclusion with previously stated outcome measures performed (timing is outlined in Table 1), as the main analysis will be an intention to treat analysis. This will, of course, be subject to the participant's continued consent to return for these assessments. Participants who withdraw consent will be advised to follow up with their regular health care provider.

Participants who are withdrawn or withdraw from active treatment will not be replaced.

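### As worded, the complete-case rule also covers the serious adverse event comparison, which conflicts with the protocol's follow-up, intention-to-treat and event-recording provisions

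*Protocol*

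**What the plan says.** The Secondary Outcomes part of the Statistical Analysis Plan covers, in order, the continuous measures, the time-to-event outcomes, the attrition and adherence model, and safety. SA events (taken here to mean SAEs) are to be reported as a cumulative incidence and "compared between treatment arms using a Poisson regression". The next paragraph opens: "Since these analyses are hypothesis generating, complete-case analyses will be used, p-values will not be listed". The Missing Data section restates it: "As secondary analyses are hypothesis generating, whole case analysis will be used even if >5% are missing data". Under Outcome Measurements, safety appears beneath the Secondary Outcomes heading and includes the "percentage of patients who experience adverse events".

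Other sections point the other way:
- Documenting participant withdrawal has everyone followed to the end of the trial, subject to consent, "as the main analysis will be an intention to treat analysis".
- Documenting Serious Adverse Events has SAEs entered in the eCRF from consent to the 26-week visit.
- Missing Data right-censors dropouts, but says so for the survival analyses only.

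**The concern.** Nothing limits the complete-case sentence to tests and questionnaires. It follows the safety paragraph immediately, and safety is classed as a secondary outcome, so a SAP written to this protocol could apply the rule to SAEs.

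For a questionnaire, an incomplete case lacks the score. For an event count, a participant who has an SAE and then leaves has a known event, and dropping that person discards it. Death is itself an SAE under the protocol's definition, and nobody who dies before week 26 can be observed to week 26. Safety is part of the first study objective, and the protocol reports estimates with intervals and no p-values, so the point estimate and the event total are what readers will see.

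**Working it through.** **The plan's own figure.** The sample size section says "A sample of 54 participants, 27 per arm, is planned for this study", based on an "expected recruitment rate of a third (33%) of glioma patients seen in recruiting clinics (163 patient per annum"). 163 × 0.33 = 53.8 and 163 / 3 = 54.3, so 54 is reproduced. Randomisation is 1:1, giving 27 per arm. The protocol gives no SAE rate and no probability of leaving after an SAE, so every event and leaving figure below is an assumption.

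**1. Illustration at the planned size.** Suppose 8 of 27 telerehabilitation and 6 of 27 usual-care participants have an SAE, one event each, and *a* and *b* of them leave before week 26. A complete case is taken to mean observed to week 26.

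- All randomised: (8/27) / (6/27) = 1.33. With SE of the log ratio √(1/8 + 1/6) = 0.540, the 95% CI is 0.46 to 3.84.
- Complete case: [(8 − a)/(27 − a)] / [(6 − b)/(27 − b)].

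| Leave after SAE (telerehab v usual care) | Complete-case data | Ratio |
|---|---|---|
| 2 v 0 | 6/25 v 6/27 | 1.08 |
| 2 v 1 | 6/25 v 5/26 | 1.25 |
| 3 v 0 | 5/24 v 6/27 | 0.94 |
| 4 v 1 | 4/23 v 5/26 | 0.90 |
| 4 v 3 (half in each arm) | 4/23 v 3/24 | 1.39 |

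For 4 v 1, the SE is √(1/4 + 1/5) = 0.671 and the 95% CI is 0.24 to 3.37. In the last row the ratio barely changes, yet 7 of the 14 recorded events are discarded.

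**2. Expected value.** With a constant event rate and a probability *q* of leaving after each event, participants who stay have event rate λ(1 − q). The complete-case ratio is therefore the true ratio × (1 − q₁)/(1 − q₀), with subscript 1 for telerehabilitation. A simulation (200,000 per arm, 0.30 SAEs per usual-care participant over 26 weeks) agrees:

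| True ratio | q₁ v q₀ | Formula | Simulated complete case | Simulated, all randomised, no offset | Simulated, all randomised, with offset |
|---|---|---|---|---|---|
| 1.33 | 0.3 v 0.3 | 1.33 | 1.33 | 1.31 | 1.33 |
| 1.33 | 0.5 v 0.3 | 0.95 | 0.95 | 1.26 | 1.33 |
| 1.33 | 0.5 v 0.1 | 0.74 | 0.75 | 1.23 | 1.34 |
| 2.0 | 0.5 v 0.1 | 1.11 | 1.11 | 1.75 | 2.00 |

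Most of the distortion comes from deleting participants. Keeping everyone, even without an offset, removes most of it.

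**3. Missing time at risk alone.** Keep everyone, with no offset, a true ratio of 1.33, and dropout unrelated to events. Mean weeks at risk are (1 − d) × 26 + d × t for a proportion *d* leaving at week *t*.

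- 20% v 20% at week 8: the ratio stays at 1.33.
- 30% v 10% at week 8: 20.6 v 24.2 weeks, so 1.33 × 20.6/24.2 = 1.13.
- 40% v 10% at week 8: 18.8 v 24.2 weeks, giving 1.04.
- 40% v 10% at week 4: 17.2 v 23.8 weeks, giving 0.96.

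The omission alone attenuates the ratio. It crosses 1 here only with large, early and unequal dropout.

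**The case against.** The strongest reply is that the rule was never meant to delete dropouts from the safety analysis. The sentence goes on to change scores and their standard deviations, and Missing Data speaks of measures and baseline values, which is the vocabulary of tests and questionnaires. Read as deleting everyone not observed to week 26, the rule would contradict the right-censoring of dropouts and empty the attrition model of the people it studies. No section says that a missed visit makes an event count missing. Therapists also relay events, and the Trial Safety, Fidelity and Implementability section summarises adverse events, dropouts and losses without a complete-case limit. Deaths also enter the survival analysis.

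Much of this stands. It shows that deletion is one reading and not a certain result, and that recorded events would probably surface somewhere in the report. It does not remove the conflict: the censoring provision is confined to survival, and the between-arm SAE comparison has no equivalent.

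A reader might also infer that the Discontinuation Criteria remove participants with a related SAE from the data. They do not. That section ends the intervention, and the withdrawal section keeps such participants under assessment, subject to consent. Nor does the missing offset amount to an error by itself: the protocol names the model without excluding an offset, and that detail is commonly left to a SAP.

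**Conclusion.** The point holds as an unreconciled conflict in the text. A stated rule reaches the SAE comparison without exemption, while other sections promise follow-up after withdrawal, intention to treat, and recording to week 26. If a complete case means observed to week 26, recorded events, including deaths, drop out of the comparison.

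The size depends on assumptions that the protocol does not supply. With 8 v 6 affected participants, the ratio of 1.33 becomes 0.90 if 4 v 1 leave, and stays close (1.39) if half leave in each arm.

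It is tempting to conclude that the safety contrast will reverse. The documents do not support that. Reversal needs both the deletion reading and markedly more leaving after harm in the arm with more harm. A more demanding programme makes unequal leaving conceivable but does not establish it. The intervals are wide either way (0.46 to 3.84 and 0.24 to 3.37), so what shifts is a point estimate and an event total, not a conclusive finding. The correction is still worth making before analysis because it is cheap and safety is a stated objective.

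**What to change.** In the Secondary Outcomes and Missing Data parts of the Statistical Analysis Plan, limit the complete-case sentences to the continuous outcome measures. Add that safety is analysed in all randomised participants, counting every recorded event up to death, withdrawal of consent, last contact or week 26, whichever comes first. This brings the analysis text into line with the withdrawal and SAE-recording sections.

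As a secondary point, preferably fit the Poisson model with log follow-up time as an offset and name when the clock starts. This can go in the SAP.

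The cost is about two sentences and the use of each participant's last-contact date. No new data collection or additional participants are needed.
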